1. *Delirium severity:* Comparison of the sum of long CAM-severity (CAM-S) score from day 2 (before treatment in the second day of the study) until day 7 (last day of evaluation). The CAM-S tool includes 10 delirium-related items, the first one being rated on a 0-1 scale and the nine followings in a 0-2 scale for a total score ranging from 0-19. The items include the four CAM items described earlier in addition to disorientation, memory impairment, perceptual disturbances, psychomotor agitation, psychomotor retardation and altered sleep-wake cycle. The sum of long CAM-S score has been shown to best reflect both 30-day and 90-day post-hospital outcomes in patients with delirium.
2. *Number of days an antipsychotic drug was administered:* as mentioned in the daily study investigator chart review.
3. *Pain:* based on twice daily Visual Analogue Scale (VAS) scores for communicating patients and FRAAC (Facial expression, Respiration, Activity, Audibility, Cry and consolability) scores for non-communicating patients. Both scales are rated on a 0-10 score and are comparable in terms of pain severity. They were routinely recorded twice daily by registered nurses.
4. *Sleep quality:* as assessed by the tenth CAM-S item.
5. *Delirium complications:* daily evaluation of falls, pulling-out intravenous or urinary catheters, new or increase in pressure ulcers grade.
6. *Length of hospital stay*
7. *Functional status at discharge:* based on Katz ADL at discharge as evaluated by study investigators.
8. *Safety and adverse events:* A checklist with acupuncture adverse events based on the AcupAE questionnaire was adapted to our study. All adverse events were recorded and monitored daily. Acupuncture-associated adverse events were discussed by the research team and the family of patients and addressed accordingly. Severe adverse events requiring patient exclusion

from the clinical trial included pneumothorax, massive bleeding, or infection in the acupoint area requiring systemic antibiotic treatment.

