**Statistical methods:** Demographic and clinical data was analyzed at baseline to measure the balance among the study groups. Quantitative variables were described using mean and standard deviation or median with range (minimum and maximum) depending on their distribution. Qualitative variables were described using frequency and percentage distributions. Next, we showed that our variables distribute equally between the two groups. For comparing normally distributed variables between our study groups, we used the t-test for independent samples. For comparing variables that do not distribute normally between our study groups, we used the Mann-Whitney test. For comparing qualitative variables between our study groups, we used the independent Chi-square test and Fisher exact test. Time-to-first delirium remission was evaluated using the Kaplan-Meier product limit survival estimator with log-rank between-group comparison and Cox regression was performed for multivariate adjustment of potential confounders. Hazard ratio (HR) with confidence intervals (CI) was calculated for each independent variable and controlled for all other independent variables in the regression. Patients who died or were discharged before day 7 had all subsequent days counted as the last day of evaluation in terms of both CAM and CAM-S. Intention-to-treat (ITT) analysis was planned to provide more information on the effect of the intervention. We explored the variables for possible collinearities, interaction, and confounders. All comparisons were two-sided with

significance level set at  $p<0.05$ . Data analysis was performed using IBM SPSS version 22 statistics software.

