## **RESULTS:**

Baseline patient data: Overall, 132 patients were screened for eligibility. Among them, 81 were recruited – 50 to the acupuncture arm and 31 to the SOC arm. Baseline sociodemographic and medical characteristics were similar in the two study arms as shown in Table 1. To note, all the patients randomized to the acupuncture arm were treated with acupuncture, while no patient assigned to the SOC arm received acupuncture (Fig. 1), so the planned ITT analysis was not required. In the acupuncture arm, 14 (28%) were censored (dead/discharged in the 7 days of follow-up), as compared with 8 (26%) in the SOC arm ( $p=0.87$ ). No difference in the baseline characteristics was noted between censored patients and patients completing the 7 days of follow-up.

Primary endpoint: Time-to-first delirium remission was shorter in the acupuncture arm as compared to the SOC arm ( $p<0.001$  for log-rank comparison, Fig. 2A). In the 7 days of evaluation, we calculated a number needed to treat (NNT) of 3 for first delirium remission. A multivariate Cox regression analysis was also conducted to evaluate the association of study arm allocation with the primary outcome (time-to-first delirium remission), adjusted for potential sociodemographic and medical confounders (age, gender, APACHE-II score, Charlson comorbidity index, number of psychotropic drugs, mobilization, cognitive impairment, reason for admission and type of delirium). The analysis showed that after adjusting for potential confounders, the time-to-first remission of delirium in the acupuncture arm was significantly shorter than in the SOC arm [HR 0.267 (95% CI 0.098-0.726,  $p=0.010$ ), Fig. 2B], while HR of potential confounders were not statistically significant. This means that acupuncture associated with SOC significantly increased the incidence of delirium remission by about 4-times, as compared to SOC only, after adjusting for sociodemographic and medical characteristics (model significance:  $p=0.042$ ). Furthermore, in the 7 days of evaluation, a significantly higher number of delirium-free days was found in the acupuncture arm [median 5.5 (0-6)] as compared with the SOC arm [median 0 (0-6)],  $p<0.001$ . Based on these results, the power of the study was calculated as 100%.

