## Secondary endpoints:

*Delirium severity:* The long CAM-S sum from day 2 to day 7 of evaluation was significantly lower in the acupuncture group [11 (24%) with no delirium, 6 (13%) with low severity, 9 (20%) with moderate severity and 19 (42%) with high severity] as compared with the control group

[3 (11%) with no delirium, 0 with low severity, 1 (4%) with moderate severity and 24 (86%) with high severity], p=0.002, Fig. 3.

*Number of psychotropic drugs-free days:* The number of psychotropic drugs-free days in the 7 days of evaluation was similar in the two study groups [median: 7 (0-7) in acupuncture arm vs 7 (0-7) in SOC arm, p=0.253].

*Pain:* No difference in daily evaluation of pain intensity was found between the two study arms in the 7 days of evaluation.

*Sleep:* According to the tenth CAM-S item daily evaluation, no difference was found in terms of quality of sleep between the study arms during the 7 days of evaluation.

*Delirium complications:* No difference was found in terms of delirium-related complications between the study arms [median: 0 (0-6) complications in acupuncture arm vs 0 (0-1) complications in SOC arm, p=0.665].

*Length of hospitalization:* The duration of hospitalization was similar in the 2 study arms [median: 13 (2-67) days in the acupuncture arm vs 12 (2-54) in the SOC arm, p=0.945].

*Functional status at discharge:* Katz ADL at discharge was similar in the two study arms [median: 2 (0-6) in the acupuncture arm vs 3.5 (0-6) in the SOC arm, p=0.945].

*Safety:* No safety event was reported according to daily AcupAE evaluation.

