## Tables and figures:

[figure not shown]
Table 1: Baseline characteristics

Baseline characteristics		Acupuncture + SOC (n=50)	SOC only (n=31)	p
Male gender – N (%)		25 (50%)	19 (61%)	0.36
Age (years) – Mean (SD)		84.0 (7.8)	85.3 (6.7)	0.45
Prevalent delirium – N (%)		26 (52%)	16 (52%)	1.00
APACHE-II – Median (min-max)		9 (5-22)	11 (6-19)	0.31
Number of medications – Median (min-max)		8 (0-16)	9 (1-15)	0.38
Number of psychotropic drugs – Median (min-max)		1 (0-5)	1 (0-3)	0.66
Mobilization – N (%)	Normal	24 (48%)	9 (19%)	0.19
	Walking aid	15 (30%)	15 (48%)	
	Wheelchair	2 (4%)	3 (10%)	
	Bedridden	9 (18%)	4 (13%)	
IQCODE – N (%)	Normal cognitive status	28 (56%)	12 (39%)	0.35
	Mild dementia	17 (34%)	16 (52%)	
	Moderate dementia	4 (8%)	3 (10%)	
	Severe dementia	1 (2%)	0	
ADL – Median (min-max)		4.5 (0-6)	4 (0-6)	0.36
Reason for admission – N (%)	Infection	19 (38%)	12 (39%)	0.94
	Dyspnea	9 (18%)	9 (29%)	
	General Deterioration	8 (16%)	4 (13%)	
	Falls	3 (6%)	3 (10%)	
	Anemia	2 (4%)	1 (3%)	
	Other	9 (18%)	2 (6%)	
Delirium category – N (%)	Hyperactive	23 (46%)	12 (39%)	0.45
	Hypoactive	15 (30%)	12 (39%)	
	Mixed	9 (18%)	3 (10%)	
	Subsyndromal	3 (6%)	4 (13%)	
Hearing and/or visual impairment – N (%)		26 (52%)	22 (71%)	0.11
Charlson Comorbidity Index – Median (min-max)		7 (4-13)	7 (4-11)	0.97
Baseline delirium severity (Long CAM-S) – Median (min-max)		8 (3-15)	9 (4-14)	0.63

[figure not shown]
Legend: ADL: Activities of Daily Living; APACHE: Acute Physiology And Chronic Health Evaluation; CAM-S: Confusion Assessment Method Severity; SOC: Standard-of-care.

Figure 1: CONSORT Flow Diagram for non-pharmacologic interventions

Legend: SOC: Standard-of-care

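### The discharge Katz ADL p-value repeats the length-of-stay p-value and is atypical for medians of 2 vs 3.5; it needs checking, and a claim of similar function is unsupported whichever p is right

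*Combined protocol and SAP*

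**What the plan says.** Functional status at discharge is the seventh listed secondary outcome (Methods, Secondary outcomes), defined as "based on Katz ADL at discharge as evaluated by study investigators". No margin for similarity accompanies the definition.

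Under Secondary endpoints, the results state "Katz ADL at discharge was similar in the two study arms" and give "median: 2 (0-6) in the acupuncture arm vs 3.5 (0-6) in the SOC arm, p=0.945". The line immediately before, on length of hospitalization, gives "median: 13 (2-67) days in the acupuncture arm vs 12 (2-54) in the SOC arm, p=0.945".

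Statistical methods says: "For comparing variables that do not distribute normally between our study groups, we used the Mann-Whitney test". Tests are two-sided. The test used for Katz ADL is not named, but reporting by median and range implies Mann-Whitney. The trial recruited "50 to the acupuncture arm and 31 to the SOC arm". The number analysed for discharge ADL is not given in the text. Table 1 has a baseline row, "ADL – Median (min-max)", with 4.5 (0-6) vs 4 (0-6) and p=0.36.

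**The concern.** Two different outcomes on consecutive lines share one p-value to three decimals. It looks natural for 13 vs 12 days. It looks odd for medians 1.5 points apart on an observed range of 0 to 6. Table 1 sharpens the doubt: a baseline gap of 0.5 points gave p=0.36, while a gap three times as large at discharge gives p=0.945.

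This p-value is the only inferential support for saying that function did not differ. Discharge function matters to patients and is one of the pre-listed outcomes. If the figure was carried over from the neighbouring line, a reported result is wrong and its replacement could read differently.

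**Working it through.** **1. Inputs.** Katz ADL at discharge: medians 2 and 3.5, both ranges 0-6, p=0.945. Length of stay: medians 13 and 12, p=0.945. Recruited: 50 and 31. Analysed n for ADL: not given, so two pairs are assumed. One is 50/30, the recruited numbers with one SOC patient fewer. The other is 45/28, the totals of the CAM-S severity categories (11+6+9+19=45; 3+0+1+24=28).

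**2. Can the printed p be reproduced?** Not from medians and ranges, because Mann-Whitney works on ranks. What can be tested is whether it is possible. With U the number of between-arm pairs in which the acupuncture score is higher (ties count half), E(U) = n1·n2/2 and Var(U) = (n1·n2/12)·[(N+1) − Σ(t³−t)/(N(N−1))], where t is the number of patients tied at each score.

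Example with n=45/28, counts at scores 0 to 6:
- acupuncture [3,7,14,5,4,4,8], median 2; SOC [7,2,0,5,10,1,3], median 3.5; both ranges 0-6
- U = 636; E(U) = 45·28/2 = 630
- Σ(t³−t) = 9,600; Var(U) = 105·[74 − 9,600/5,256] = 7,578; SD = 87.05
- z = 6/87.05 = 0.069; two-sided p = 0.945

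Example with n=50/30: [6,4,16,4,5,6,9] vs [7,2,2,4,9,1,5] gives U = 757, E(U) = 750, SD = 99.19, z = 0.071, p = 0.944.

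So the printed figures can coexist.

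**3. How far do the summaries constrain p?** Hardly at all. With n=50/30 and the same medians and ranges, [2,2,23,5,7,3,8] vs [4,3,3,5,14,0,1] gives p = 1.0, while [1,0,48,0,0,0,1] vs [1,0,0,14,1,0,14] gives p below 1e-12.

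**4. How usual is a value this high?** Whole-point scores from 0 to 6 were drawn from random (Dirichlet) score distributions, either common to both arms or separate. Only datasets matching both medians and both ranges were kept.

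| n | Score distribution | Concentration | Datasets kept | Median p | p≥0.90 | p<0.05 |
|---|---|---|---|---|---|---|
| 50/30 | common | 0.5 | 125 | 0.395 | 5.6% | 6.4% |
| 50/30 | common | 1 | 333 | 0.306 | 3.0% | 8.1% |
| 50/30 | common | 3 | 817 | 0.227 | 2.4% | 11.3% |
| 50/30 | separate | 0.5 | 154 | 0.136 | 4.5% | 35.7% |
| 50/30 | separate | 1 | 492 | 0.130 | 3.9% | 36.0% |
| 50/30 | separate | 3 | 1,312 | 0.119 | 2.1% | 31.1% |
| 45/28 | common | 0.5 | 134 | 0.431 | 9.0% | 8.2% |
| 45/28 | common | 1 | 417 | 0.363 | 4.6% | 5.5% |
| 45/28 | common | 3 | 995 | 0.266 | 3.3% | 7.7% |
| 45/28 | separate | 0.5 | 163 | 0.128 | 3.1% | 33.1% |

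Further runs widened the share with p≥0.90 to about 2-12%. A value this high is uncommon even when both arms share one distribution, the assumption kindest to the printed figure.

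**5. Denominator.** The median of an odd number of whole-point scores is one of those scores, so it is a whole number. A median of 3.5 needs an even n, and 31 is odd. On whole-point scoring, at least one SOC patient is therefore outside the comparison. The baseline medians (4 with n=31, 4.5 with n=50) fit whole-point scoring.

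**6. Deaths.** The Results pool death and discharge within 7 days (14 vs 8). The carry-forward rule in Statistical methods covers only CAM and CAM-S. Nothing states how in-hospital deaths enter discharge ADL.

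**The case against.** The strongest reply is that no arithmetic error is shown. Mann-Whitney compares ranks, and step 2 gives datasets with exactly the printed medians and ranges and p of about 0.945. In those datasets the ranks lean very slightly towards acupuncture, so even the direction suggested by the medians is not secure. This stands. A reader might infer that the p-value is impossible; the documents do not support that.

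The simulated shares depend on assumed score distributions and assumed n, which also stands. They support a range and a suspicion, not a replacement p. In every setting the typical p exceeds 0.05, so a corrected value may leave non-significance unchanged.

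A reader might also subtract the printed medians (4.5 to 2, and 4 to 3.5) and infer a larger functional loss with acupuncture. A difference between group medians is not a median change within patients, and the discharge subset may differ from the baseline one. Nor does anything show that an unfavourable result was concealed, or which of the two lines, if either, was copied.

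The denominator argument needs whole-point scoring, which the documents do not state. The flow diagram, not available in the text reviewed, may report the numbers analysed. Finally, adjustment for baseline goes beyond the planned unadjusted test. It is nevertheless a modest request, since baseline ADL was collected and an estimate with an interval is needed anyway. None of these replies supports the claim of similarity.

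**Conclusion.** The point holds as a verification and reporting issue on one secondary outcome. The exact repetition is a fact of the text. That 0.945 is atypical for these medians (p≥0.90 in about 2-12% of matching datasets, typical p about 0.1 to 0.4) rests on whole-point scoring from 0 to 6, on n of 50/30 or 45/28, and on the Mann-Whitney test. Together these make a transcription error a fair suspicion and no more.

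The unsupported claim of similarity does not depend on that suspicion. With at most 50 and 31 patients, a non-significant p does not establish similarity, and no n, estimate, interval or margin is given. The only visible direction is against acupuncture. That is a reason to report the comparison properly, not evidence of harm.

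**What to change.** - Check both p=0.945 entries against the source output and correct whichever is wrong. If both are right, say so and name the test.
- Report the number analysed per arm for discharge ADL, the number of in-hospital deaths per arm, and how those deaths were handled.
- Add interquartile ranges, and compare discharge ADL adjusted for baseline ADL, with an estimate and 95% CI.
- Replace the statement of similarity with wording that the interval supports.

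The cost is a few lines of analysis on data already held. The reported conclusion on function may become less favourable, or simply less certain.

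### The reported safety result is a zero on an acupuncture checklist with no arm, denominator or interval, and the text gives neither deaths nor general adverse events by arm

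*Combined protocol and SAP*

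**What the plan says.** In the Combined protocol and SAP, Methods, Secondary outcomes, item 8 (safety and adverse events) describes the instrument as "A checklist with acupuncture adverse events based on the AcupAE questionnaire", adapted to the study. The next line reads "All adverse events were recorded and monitored daily". The item then turns to acupuncture-associated events. Its sentence on severe events requiring exclusion continues "from the clinical trial included pneumothorax, massive bleeding, or infection in the acupoint area requiring systemic antibiotic treatment".

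The result, under Secondary endpoints, Safety, is a single sentence: "No safety event was reported according to daily AcupAE evaluation". It names no arm and no number assessed.

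Deaths are mentioned in two other places. Results, Baseline patient data says "In the acupuncture arm, 14 (28%) were censored (dead/discharged in the 7 days of follow-up", against 8 (26%) in the SOC arm, p=0.87. Methods, Statistical methods applies one carry-forward rule to CAM and CAM-S after either death or discharge.

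A further harm outcome, delirium complications (item 5: falls, pulled-out lines or catheters, pressure ulcers), is compared between arms in the Results: median 0 (0-6) with acupuncture and 0 (0-1) with SOC, p=0.665.

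**The concern.** These patients have a mean age of 84.0 and 85.3 years (Table 1). For them, death and general adverse events are basic measures of harm, and a trial of an added treatment should let the reader compare them between arms. The safety sentence does not do this. It concerns one instrument aimed at needling and makes no comparison. The only figure in the text that includes deaths mixes them with discharges, which are usually a favourable exit. A similar combined percentage in the two arms could hide quite different numbers of deaths.

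What is at stake is the safety conclusion. An unqualified zero with no denominator or limit can be taken for evidence that harm was compared and found absent.

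**Working it through.** **Inputs.** Arm sizes: "81 were recruited – 50 to the acupuncture arm and 31 to the SOC arm". Dead or discharged within 7 days: 14 and 8 (Results, Baseline patient data). The same paragraph says that every patient in the acupuncture arm was treated, so 50 is the natural exposed denominator. The Safety sentence states none.

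**1. The combined count.** 14/50 = 28.0% and 8/31 = 25.8%, as printed. Together they are 22/81 = 27.2%. Pearson chi-square without correction is 81 × (14×23 − 36×8)² / (50×31×22×59) = 81 × 34² / 2,011,900 = 0.0465, p = 0.829. The likelihood-ratio test also gives 0.829; Yates and Fisher give 1.00. The printed 0.87 is not reproduced, but every version is far from significance and the gap does not bear on this point. The risk difference is +2.2 percentage points (Newcombe 95% CI −18.2 to +20.4), so even the combined count is imprecise.

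**2. What the combined count allows for deaths.** The text gives no deaths by arm, so only bounds can be shown. Assume 0 to 14 deaths among 50 and 0 to 8 among 31, which is 15 × 9 = 135 possible pairs.

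- All acupuncture exits are deaths and no SOC exit is: 14/50 vs 0/31, difference +28.0 points, Fisher p = 0.0006.
- The reverse: 0/50 vs 8/31, difference −25.8 points, Fisher p = 0.0002.
- 29 of the 135 pairs give Fisher p < 0.05, 14 with fewer deaths on acupuncture and 15 with more. The smallest counts that do so are 0/50 vs 4/31 (p = 0.019) and 7/50 vs 0/31 (p = 0.040).

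The pairs are not equally likely, so 29/135 is not a probability. The bounds show only that similar combined percentages do not settle the question for deaths. Deaths in hospital after day 7 are a further gap: 81 − 22 = 59 patients were neither dead nor discharged within the 7 days.

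**3. The zero count.** For 0 of n, the exact two-sided 95% upper limit is 1 − 0.025^(1/n). With n = 50 this is 7.1% (one-sided 5.8%). The documents do not say whether the checklist was used in the SOC arm. If it was, with no events, the SOC limit with n = 31 would be 11.2%.

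**4. What the zero refers to.** The complication ranges reach 6 and 1, so at least one patient in each arm had a fall, a pulled-out line or catheter, or a pressure ulcer event. The zero in the Safety sentence therefore cannot mean no untoward event of any kind. It can only mean no checklist event.

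**The case against.** The strongest reply is that the sentence already limits itself to the AcupAE evaluation, that the Methods define this as an acupuncture checklist, and that the documents claim no equivalence of the arms on safety. This is fair as to wording. It does not supply the missing arm, denominator, interval or deaths.

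Several stronger readings are tempting, and the documents do not support them:

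- *The safety result itself merges deaths with discharges.* It mentions neither. The merging is in the follow-up sentence and the carry-forward rule.
- *Deaths are reported nowhere by arm.* Figure 1, the CONSORT flow diagram, is not visible here and is a natural place for the split. The statement can be made for the text only.
- *Harm was not compared at all.* Complications were compared, though only as a pooled median count that excludes death.
- *General adverse events were collected and then left out.* The line on recording all adverse events follows the checklist sentence directly and may mean checklist events only.
- *The checklist could not yield a comparison.* Its items are not given, and its use in the SOC arm is not stated. All that can be said is that no comparison is reported.
- *Deaths were imbalanced.* The figures of −25.8 and +28.0 points are arithmetic limits, not evidence.

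It also stands that in-hospital mortality is not a listed outcome, and that the plan does not require a confidence limit on a zero count.

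**Conclusion.** The point holds for the readable text. The safety outcome is reported only as zero events on an acupuncture-specific checklist. Seven-day deaths cannot be separated from discharges among the 22 of 81 patients (27%) who left early, and neither deaths nor general adverse events are compared between arms. As reported, the trial can say that no acupuncture-related checklist event was seen, compatible with a true rate of up to 7.1%. It cannot say that harm overall was similar in the two arms.

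This rests on two assumptions: that all 50 treated patients were assessed with the checklist, and that Figure 1 does not already split deaths from discharges. If Figure 1 does, what remains on 7-day deaths is to state the split in the Results. This is a gap in the reported safety analysis that should be closed. It does not touch the primary result.

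**What to change.** - Report deaths within 7 days separately from discharges, by arm, with exact 95% confidence intervals. If Figure 1 already has the split, state it in the Results.
- Tabulate by arm any adverse events recorded beyond the checklist. If none were collected, clarify in item 8 that only checklist events were recorded.
- Give in-hospital deaths by arm if the records hold them, labelled as descriptive because they are not a listed outcome.
- State the checklist result as no acupuncture-related event in 50 treated patients (0/50, exact two-sided 95% upper limit 7.1%), after confirming the denominator, and say whether the checklist was used in the SOC arm.

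The cost is small. Seven-day deaths must have been known for patients to be counted as dead or discharged, although in-hospital deaths and events beyond the checklist may need a search of the records. The price is a less absolute safety statement.
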